| Duration of study for each subject | 
Up to 60 months
 
Subjects will participate in up to 3 possible study visits over a total of 5 years. Duration of time since vaccination as part of CTN 236 varies depending on when they were enrolled; therefore, to ensure all subjects are offered participation in the long term follow up, 6 possible visit times have been created.
 |
| Visit schedule | Main Study Procedures (no standard clinical or sub-study procedures) |

| | Informed Consent/ Assent | Health Questionnaire | Study Blood Work | Cytology and HPV DNA & vaginal swabs* | SAE and Con Med Assessment |
|------------------------|-----------------------------|----------------------|------------------|---------------------------------------|----------------------------|
| Month 36 (Visit 8) | X | X | X | X | X |
| Month 48 (Visit 9) | X | X | X | X | X |
| Month 60 (Visit 10) | X | X | X | X | X |
| Month 72 (Visit 11) | X | X | X | X | X |
| Month 84 (Visit 12) | X | X | X | X | X |
| Month 96 (Visit 13) | X | X | X | X | X |

* Those girls and women who are pre-menarchal or never sexually active will not have any pelvic examinations, clinical Pap smears, or study genital sampling until post-menarchal and sexually active.

Complete outline of all procedures found in table 7.3

| | |
|--|---|
| Data collection | Template recruitment documents, consent and source documents will be provided by the Study Coordinating Centre. Source data will be transferred to paper case report forms and sent to the CIHR Canadian HIV Trials Network (CTN) where it will be entered into an electronic database. |
| Monitoring | This study is being conducted according to the following: International Committee on Harmonization (ICH) Guidance Document E6: Good Clinical Practice (GCP): Consolidated Guidelines. Site monitoring will be performed to ensure compliance with the above. |
| Data Safety Monitoring Board (DSMB) | The established CTN data safety monitoring committee with additional expertise in pediatrics and gyne-oncology will provide oversight and monitoring of the conduct of the study to ensure the safety of the subjects. Additionally, the DSMB will ensure the validity and integrity of the study data. |

LIST OF ABBREVIATIONS

| | |
|--------------|---|
| AE | Adverse event |
| AIDS | Acquired immunodeficiency syndrome |
| ART | Antiretroviral therapy |
| ARV | Antiretroviral |
| BCCDC | British Columbia Centre for Disease Control |

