The two currently licensed vaccines designed to prevent HPV infection, have been tested in large clinical trials. There is a bivalent vaccine against HPV 16 and 18 (GlaxoSmithKline, GSK) and a quadrivalent vaccine against HPV 6, 11, 16 and 18 (Merck). In addition, a 9-valent vaccine is currently being investigated in large scale clinical trials, with positive safety, immunogenicity and efficacy data under review by the FDA. These vaccines are produced as virus-like particles (VLP's) based on the L1 capsid protein gene of the virus inserted in insect or yeast vectors. These proteins self-assemble into protein shells with identical configuration to the native virus, but without DNA, and so are deemed subunit, protein vaccines. Safety, efficacy, and immunogenicity data on these vaccines in HIV-negative populations of young women are based on clinical trials conducted by GSK and Merck, respectively, with some follow up post-licensure trials now in progress. Both have shown remarkable safety profiles in otherwise healthy young HIV-negative women, with limited local injection site reactions as the primary side-effect and no evidence for differences in serious adverse events between vaccine and placebo arms.⁶⁵

Immunogenicity to the quadrivalent vaccine has been well studied in HIV-negative populations, showing that anti-HPV 6, 11, 16 and 18 geometric mean titers (GMT) were highest at month 7 (1 month following the final dose 3). Anti-HPV GMT's declined thereafter but reached a plateau at month 24 and remained stable through 5 years.^{66,67,68} In the original immunogenicity study by Villa et al.,⁶⁷ 100% of the subjects who were antibody negative to the relevant HPV type at baseline had a detectable antibody response at month 7 to HPV 6, 11, 16 and 18 respectively. These levels were 10-to 10⁴-fold higher than natural antibody levels in placebo recipients who were vaccine type positive at baseline.

8. **HPV vaccine implementation**

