Antibody response to HPV types 6, 11, 16 and 18 has been collected and analyzed on over 1500 serology samples for months 0, 7, 12, 18 and 24. Seroconversion rates at month 7 were approximately 93-98% in this HIV-positive population, much higher than anticipated. However, peak Geometric Mean Titres (GMT) were lower than in HIV negative populations. In addition this was associated with a significant decline in antibody levels by month 24, particularly to HPV18. Similar to our findings, Kahn et al., also showed that level of antibody was lower in individuals not on cART in their open label 16-23 year old study of 99 women given the q HPV vaccine.⁸⁰ Of note, we also observed statistically significantly higher levels of incident and persistent infections of vaccine containing types in a short term follow up period. This preliminary data outlines the importance of following this established cohort for long-term immunogenicity. When directly comparing the school based vaccine target age of 9-13 years, the HIV positive girls had a statistically significantly lower peak GMT than age matched HIV comparators.^{81,82} Similar studies conducted by other investigator groups have preliminary data available as well. Weinberg et al, showed that in HIV infected 7-12 year old children, there was a good seroconversion rate at > 94% but noted that the level of antibody to HPV18 was less than for the other genotypes. They also added a fourth dose of the vaccine which demonstrated an appropriate anamnestic response suggesting that should a booster be deemed necessary it should function to appropriately enhance the antibody response.⁸³ A South African based study of the bivalent vaccine demonstrated safety and 100% seroconversion to the vaccine containing serotypes regardless of CD4, HIV viral load and HIV clinical stage of disease.⁸⁴

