4.0 STUDY DESIGN & METHODS

1. Design

This prospective longitudinal cohort study will evaluate the effectiveness of a quadrivalent HPV VLP vaccine in an HIV-positive cohort of girls and women in multiple centres across Canada.

2. Rationale

This study presents a unique opportunity to understand the long term impact of HPV vaccination in immune compromised women. Our prior study demonstrated that although women and girls living with HIV in Canada have complicated lives and have a high burden of socioeconomic disadvantages, they are very interested and committed to participating in research. This is clearly demonstrated by the degree of engagement of positive women in the National Consensus Statement on Women, Trans People and Girls and HIV Research in Canada. Our study sites across the country have been highly effective at engaging with this challenging population

through their long-standing, dedicated clinics. We have a cohort of over 400 girls and women who continue to live with their HIV disease and will require ongoing specialized HIV care for the rest of their lives. As they are just completing the first protocol out to 24 months and are for the most part still attending for care, with 94% remaining engaged with our study groups. We are confident that we can effectively re-engage them in our follow-up study. It is vital that this study be launched now while most participants are at 24-36 months from vaccine course, and key follow up timed sampling can ascertain the trajectory of antibody responses as well as the course of HPV disease.

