5.0 STUDY COHORT

1. Population

Four hundred and seven (407) HIV-positive girls and women (greater than, or equal to, age 11) attending the HIV treatment clinics in each of the 13 sites across Canada and who have enrolled in the original study “A Study of an HPV VLP Vaccine in a Cohort of HIV Positive Girls and Women (CTN 236)” will be offered participation in the study.

Inclusion Criteria

- Enrolled in CTN 236 study
- Able to give fully informed consent or assent

Exclusion Criteria

- Did not receive at least one vaccination via CTN 236, phase 1
- Cannot provide fully informed consent or assent

2. Delays and contraindications to subsequent study procedures

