12.1.2 Merck laboratory Serotesting Methods

Serum anti-HPV 6, 11, 16, and 18 immunoglobulin levels will be measured using a competitive Luminex immunoassay (cLIA), and reported in arbitrary units (milli-Merck Units per millilitre or mMU/ml) relative to the standard curves generated for each individual HPV type.⁸⁶ The HPV cLIA uses yeast-derived HPV L1 6, 11, 16 and 18 VLPs that have been covalently conjugated to Luminex microspheres. The type specific HPV-VLP antibody responses are associated with specific Luminex microspheres that are identified by their distinct fluorescent dye spectral properties. Antibody titers are determined in a competitive format, where known, with type-specific labeled neutralizing antibodies for each type competing with patient serum antibodies for binding to conformation-sensitive neutralizing epitopes on the VLPs. For each HPV type, relative inhibition is compared to a pooled standard reference serum. Seropositivity will be defined in this assay as > 20 mMU/ml for HPV 6, 16 mMU/ml for type 11, 20 mMU/ml for 16 and 24 mMU/ml for 18. Of note, lower limits of detection for this assay are 8.0, 8.0, 12.0, and 8.0 mMU/ml for 6, 11, 16 and 18 respectively.⁶⁷

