16.0 STATISTICAL ANALYSIS

1. Statistical Analysis Plan

Demographics: Characteristics of the study population will be described with frequencies and proportions for categorical variables, means and standard deviations for normally distributed continuous variables and medians and interquartile ranges for skewed continuous variables.

2. Primary Analysis

For each of the four vaccine containing HPV types, antibody response will be summarized using GMT's calculated for age specific groups within the HIV-positive cohort. Specific age groupings have been chosen to permit age matched HIV comparisons.

- a) Antibody response for subjects aged 9-13 and those aged 16-26 will be compared to the individual patient level data from an HIV-negative cohort 86 using Wilcoxon rank-sum tests. The age adjusted fold-difference in GMT

between HIV-positive and HIV-negative populations will be calculated using generalized linear models. For women over age 26, the type specific HPV GMT will be compared to GMTs in the published literature using a sign test.

- b) Within the HIV-positive cohort, predictors of decline from peak antibody response among HIV-positive girls and women will be determined using generalized linear models. Potential covariates to be considered in these models are age, HSV-2 status, substance use, CD4 count, HIV viral load and antiretroviral status at the time of first vaccination, and CD4 nadir.
- c) Longitudinal analyses will be conducted to describe the effect of HIV on antibody response at the visits at 36, 48, 60, 72, 84, and 96 months post first vaccine dose. Generalized estimating equation (GEE) models with a unity link will be used to adjust for correlation among repeat observations within study participants. Individual level data on HIV-negative girls and young women will be available at 36, 48, 60, 72, 84 and 96 months post first vaccine dose. After adjusting for age, an interaction between HIV and time since first dose will be included in the model to test for a difference in the degree of waning of response in addition to the strength of the initial response. GEE models will also be fit for the HIV-positive girls and women alone to examine the associations.

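### For women over 26, the sign test against published GMTs ignores the error in the published value, so its false-positive rate can exceed 5%

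*Combined protocol and SAP*

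**What the plan says.** Section 16.2 a) treats the age groups differently. For ages 9-13 and 16-26 it has individual HIV-negative data, rank-sum tests and an age-adjusted fold-difference in GMT. For women over 26 it has one sentence: "the type specific HPV GMT will be compared to GMTs in the published literature using a sign test". No publication, reference population, month after vaccination, reference size or significance level is given for that comparison, and none is designated elsewhere. The Background and the Rationale in section 4.0 mention published qHPV titres only in general terms.

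Item c) adds a longitudinal model with an interaction between HIV and time. Its HIV-negative data are on younger participants: "Individual level data on HIV-negative girls and young women will be available".

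Section 5.0 offers participation to "Four hundred and seven (407) HIV-positive girls and women" aged 11 and over. The number over 26 is not stated. Section 12.1.2 says that the "lower limits of detection for this assay are 8.0, 8.0, 12.0, and 8.0 mMU/ml" for types 6, 11, 16 and 18, but section 16 has no rule for coding titres below these limits.

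**The concern.** A one-sample sign test counts how many women lie above and below a fixed value. Here that value is itself an estimate from a finite sample. If the published GMT is somewhat high by chance, too many women fall below it, and the test can read this as an effect of HIV. The rank-sum tests for the younger groups do not have this fault, because they count the sampling error on both sides.

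Two further features add to the problem. The test concerns the median, whereas the plan speaks of the GMT; the two agree only if log titres are symmetric. And the test does not say how large the difference is: a point ratio could be formed from the planned GMTs, but no interval that allows for the reference's error comes with it.

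This is the only comparison that item a) names specifically for women over 26, so it is likely to carry what is reported about HIV and antibody level in that age group.

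**Working it through.** **Inputs.** The documents state no alpha, sidedness, cohort number or reference size for this test, so there is no figure of the plan's to reproduce. Assumed: two-sided 5%; normal log titres with the same mean and SD in both populations (no true difference); n women over 26; a published GMT from m women. The only sizes in the documents are the 407 of all ages and the limit in the Summary: "Subjects will participate in up to 3 possible study visits over a total of 5 years". If all 407 attended three of the six visit times, the average would be 407 x 3/6 = 203.5 per visit time. That is not a cap, because the Rationale says that "most participants are at 24-36 months from vaccine course", so attendance may bunch. I use n = 50 to 200.

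**Reading of the test.** The signs must be counted over women. Counted over the four HPV types, the smallest two-sided p-value would be 2 x 0.5^4 = 0.125, and the test could never reach 5%.

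**Method.** In SD units the published mean log titre has error Z/sqrt(m), with Z standard normal. Given Z, the chance that a woman's titre exceeds the published value is Phi(-Z/sqrt(m)) instead of 0.5. The exact test rejects when the rarer sign occurs at most 17 times of 50, 39 of 100, 62 of 150 or 85 of 200. The rejection probability is averaged over Z. The SD cancels.

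A large-sample form shows why the ratio n/m matters: rate = 2 x (1 - Phi(1.96/sqrt(1 + (2/pi) x n/m))). At n = m this is 2 x (1 - Phi(1.96/1.279)) = 12.6%. The exact rates are lower because the discrete test is conservative: with an error-free reference it rejects 3.3% (n = 50), 3.5% (100), 4.1% (150) and 4.0% (200) of the time.

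**Exact false-positive rates.**

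| Cohort n vs reference m | Rate |
|---|---|
| 50 vs 50 | 9.4% |
| 100 vs 100 | 9.9% |
| 150 vs 150 | 11.0% |
| 200 vs 200 | 10.8% |
| 150 vs 100 | 14.3% |
| 200 vs 100 | 17.3% |
| 100 vs 300 | 5.6% |
| 150 vs 300 | 7.5% |
| 200 vs 300 | 8.5% |
| 200 vs 500 | 6.7% |
| 50 vs 200 | 4.7% |
| 100 vs 500 | 4.7% |
| 200 vs 1000 | 5.3% |

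The rate falls to 5% once m exceeds about 160 at n = 50, 400 at n = 100, and 1300 at n = 200.

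**Median versus GMT.** Suppose a share q of the reference titres lies below the detection limit and is coded at the limit. With c the q-quantile of the standard normal, the published mean then lies phi(c) + c x q SDs above the median. For q = 10% this is 0.1755 - 1.2816 x 0.10 = 0.047; for q = 20% it is 0.2800 - 0.8416 x 0.20 = 0.112. The rate rises from 5.6% to 6.6% or 13.0% at 100 vs 300, and from 8.5% to 10.9% or 24.4% at 200 vs 300.

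Half-limit coding lowers the published mean by a further q x log10(2)/SD. At an assumed log10 SD of 0.55 that is 0.10 x 0.547 = 0.055 or 0.20 x 0.547 = 0.109, which nearly cancels the shift (net -0.008 or +0.003 SD). Over SDs of 0.45 to 0.65 and shares of 5-20%, the rates are 5.5-5.9% at 100 vs 300 and 8.3-9.3% at 200 vs 300, close to those without any titres below the limit.

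**A test that counts the reference's error.** A comparison of mean log titres that uses the published standard error rejected in about 5% of simulated runs (4.9-5.2%) at 200 vs 100, 200 vs 200 and 200 vs 1000.

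**The case against.** The strongest reply is that nothing in the documents fixes n or m. With a large published study the test holds its level, so the fault may never appear. That stands, and it is why the point says only that the rate can exceed 5%.

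The reply can also point to the size of the error and the role of the comparison. At m = 100 and a log10 SD of 0.55, one standard error of the reference is 0.55/10 = 0.055, about 1.13-fold. The primary objective in section 3.0 is to measure the response, and item c) tests faster decline. This too stands. The point does not affect that hypothesis test.

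The sign test has merits. Titres below the limit in the cohort do not disturb it as long as the published GMT is above the limit. It can also be inverted to give an interval for the median, which becomes an interval for the GMT ratio if log titres are symmetric. But that interval still leaves out the reference's error, which is the main fault.

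The fold-difference model in item a) might be thought to cover the older women. However, the individual HIV-negative data that the plan describes are for ages 9-13 and 16-26 and, in item c), for girls and young women.

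A reader might infer that loss of antibody makes the detection limit the main problem, with error rates of 13-24%. The documents do not support this. The decline that the Background calls "associated with a significant decline in antibody levels by month 24, particularly to HPV18" was seen in the HIV-positive cohort, whereas the bias depends on the HIV-negative reference. For HIV-negative women the Background reports GMTs that are stable from month 24 through 5 years. No share below the limit is given for either population, and the effect nearly vanishes under half-limit coding.

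**Conclusion.** The concern holds, conditionally. The planned test leaves out the sampling error of the published GMT, and its nominal level is met only when the reference is several times larger than the group over 26. Under the stated assumptions the false-positive rate is 9-11% at equal sizes of 50 to 200, 14-17% at 150 or 200 vs 100, and 5.6-8.5% at 100 to 200 vs 300. Asymmetry from titres below the limit could add to this if the reference coded them at the limit, and hardly does if it used half the limit.

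It would be wrong to infer that the error rate is certainly inflated, or that the study's hypothesis of faster decline is at risk. The sizes are unknown, and this is a supporting comparison. Still, a better method is available for little effort, so the sentence should be changed before analysis.

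**What to change.** Replace the sentence on women over 26 in section 16.2 a) with:

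> For women over age 26, each type-specific GMT will be compared with the GMT from one published HIV-negative qHPV reference (cLIA, mMU/ml), chosen and cited before analysis and used for all visits, at the matching month after first dose. The result is a GMT ratio with 95% CI on the log10 scale, with SE^2 = s^2/n + SE_ref^2, where SE_ref comes from the published 95% CI, (log10 upper - log10 lower)/3.92, or from the published SD and n. Titres below the detection limit are coded by the reference's own rule; if it is not stated, half-limit coding is used and limit coding is shown as a sensitivity analysis. Where the reference gives no CI or SD, or no matching month, the ratio is descriptive without a p-value.

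Only the analysis text changes; no new data are needed. There are three costs. First, with equal SDs the interval is wider than one that ignores the reference's error by sqrt(1 + n/m): sqrt(2) = 1.41 times at 100 vs 100, and sqrt(1.333) = 1.15 times at 100 vs 300. Second, the ratio depends on how titres below the limit are coded, hence the sensitivity analysis. Third, the documents do not show that a suitable reference exists at months 36-96; if none does, the comparison is descriptive only.

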11.0 SUBJECT COMPLETION AND WITHDRAWAL

Investigators or their delegates will attempt to contact those study subjects who do not return for study visits. Study personnel will make at least three attempts to contact the subject using various communication means. Each attempt should be documented in the subject source documents.

A subject completing three annual visits up to and including Month 96/Visit 13 will be considered to have completed the study.

Withdrawals will not be replaced. All withdrawals will be documented including the date of the withdrawal and the reason.

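### The waning test (16.0, item c) is an unweighted GEE with no method for missed visits, withdrawal or non-return; its HIV-by-time term may be biased, with direction and size unverified

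*Combined protocol and SAP*

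**What the plan says.** Section 16.0, Primary Analysis item c), compares antibody response over Months 36 to 96 between HIV-positive and HIV-negative participants. On method: "Generalized estimating equation (GEE) models with a unity link will be used to adjust for correlation among repeat observations within study participants". On the hypothesis test: "After adjusting for age, an interaction between HIV and time since first dose will be included in the model to test for a difference" in waning. For the comparator: "Individual level data on HIV-negative girls and young women will be available" at the same time points. The model as described therefore contains HIV group, time and age. No weights, working correlation or titre scale are given.

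Measures of HIV control appear in item b), on decline from peak: "CD4 count, HIV viral load and antiretroviral status at the time of first vaccination, and CD4 nadir" are among its candidate covariates. Item c) adds GEE models within the HIV-positive cohort alone, but its HIV-by-time model lists no measure of HIV control.

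Section 11.0 covers loss to follow-up operationally: "Study personnel will make at least three attempts to contact the subject using various communication means", and "Withdrawals will not be replaced. All withdrawals will be documented including the date of the withdrawal and the reason". Section 16.0 contains no missing-data assumption, weighting, imputation, comparison of leavers with stayers, or dropout sensitivity analysis. It also does not address women in CTN 236 who do not join the follow-up.

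**The concern.** Item c) is the model that tests the central hypothesis in Section 2.0, that antibody declines faster in HIV-positive girls and women. An ordinary GEE uses the visits that took place. It generally needs the missing visits to be unrelated to titre once the model covariates are taken into account, and here those are only HIV group, time and age.

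A variable outside the model could break that condition. The Background reports, from the group's own data and another study, that "level of antibody was lower in individuals not on cART". The hypothesis adds that HIV parameters determine the decline. If HIV control also affects who attends, late HIV-positive visits would come from a selected group and the interaction would reflect selection as well as waning. An interaction near zero could then mean durable antibody or selective loss, and the planned analysis could not tell these apart.

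**Working it through.** The documents give no sample size, power, standard deviation, slope or dropout allowance, so there is no planned figure to reproduce.

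**Step 1. Retention.** Section 4.0 reports 94% still engaged at about 24 months, and Section 5.0 gives 407 women. If the 94% applies to the 407, then 0.94 × 407 = 382.58, about 383 engaged and 407 − 383 = 24 not. This figure predates Months 36 to 96 and is not split by HIV control.

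**Step 2. Missingness by design.** Each woman has up to three of six visit times, depending on when she was vaccinated. That part is harmless if date of first dose is unrelated to titre. The issue is visits that were due and not attended.

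**Step 3. Illustrative simulation.** Every input is an assumption: 300,000 per group; entry at Month 36, 48, 60 or 72 at random; three annual visits; 25% of HIV-positive women uncontrolled, with log10 titre 0.3 lower and falling 0.06 per year faster; slopes of −0.06 per year (controlled) and −0.03 (HIV-negative). Standard deviations are 0.45 between women, 0.03 for slopes and 0.15 within women. HIV-negative dropout is 5% per year unless stated.

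True interaction = [0.75 × (−0.06) + 0.25 × (−0.12)] − (−0.03) = −0.075 + 0.03 = −0.045 log10 per year.

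Bias = (estimate ÷ true − 1) × 100, taken before the slopes below were rounded. A minus sign means waning is understated.

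| Assumed annual dropout in HIV-positive women | True | Independence | Exchangeable | Weighted |
|---|---|---|---|---|
| 6% for all | −0.0452 | −0.0459 (+2%) | −0.0454 (0%) | −0.0459 (+2%) |
| 15% uncontrolled, 5% controlled | −0.0447 | −0.0400 (−10%) | −0.0423 (−6%) | −0.0442 (−1%) |
| 25% uncontrolled, 5% controlled | −0.0450 | −0.0364 (−19%) | −0.0400 (−11%) | −0.0448 (0%) |
| 15% and 5%, also rising as last titre falls | −0.0450 | −0.0319 (−29%) | −0.0403 (−10%) | −0.0458 (+2%) |
| 15% and 5%, lower level only, same slope | −0.0300 | −0.0287 (−4%) | −0.0299 (−1%) | −0.0308 (+3%) |
| 15% and 5%, faster slope only, same level | −0.0452 | −0.0424 (−6%) | −0.0427 (−5%) | −0.0445 (−1%) |
| Reverse: 5% uncontrolled, 15% controlled | −0.0449 | −0.0493 (+10%) | −0.0472 (+5%) | −0.0446 (−1%) |
| Titre-related dropout in both cohorts, base 8% | −0.0451 | −0.0413 (−8%) | −0.0436 (−3%) | −0.0442 (−2%) |

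The first row shows that differences of about 2% are simulation noise. Rows two to four, where uncontrolled women have both lower titres and faster waning, give 6% to 29% understatement. The weighted column used the true attendance probabilities under working independence. It shows what weighting can do when the drivers are measured, not that it will succeed here.

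**Step 4. Absolute size.** The smallest loss in rows two to four is 0.0447 − 0.0423 = 0.0024 log10 per year; the largest is 0.0450 − 0.0319 = 0.0131. Over the five years from Month 36 to 96 these are 5 × 0.0024 = 0.012 and 5 × 0.0131 = 0.0655 log10, or titre ratios of 10^0.012 = 1.03 and 10^0.0655 = 1.16.

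**The case against.** The strongest reply is that the key link is undocumented. Nothing says that women with uncontrolled HIV leave more often. Section 4.0 does state that "women and girls living with HIV in Canada have complicated lives and have a high burden of socioeconomic disadvantages", but the same sentence goes on to describe strong interest in and commitment to research, and the 94% engagement figure follows. That is the only retention evidence in the documents, and it is favourable. The antibody finding off cART concerns level rather than rate of decline, and with a level difference alone the bias was only 1% to 4%. Faster waning with poor HIV control is the hypothesis under test. Exchangeable correlation also reduced the bias in every differential-dropout row.

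All of this stands, and it limits what can be claimed about direction and size. It does not supply a method. The 94% describes an earlier period, contact attempts do not repair an analysis, and the working correlation is not stated. The HIV-control covariates in item b) do not enter the HIV-by-time test.

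Three stronger readings are tempting:

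- A reader might infer that the HIV-negative cohort is free of selective loss. Its attrition is not described, so this cannot be said.
- A reader might infer that data collection ceases entirely when visits stop. Section 11.0 does not say so, and Section 9.0 requires deaths during the study to be reported.
- A reader might expect a much larger proportional bias. That follows from assuming that controlled HIV-positive women wane no faster than HIV-negative women, which shrinks the denominator. The documents give no slopes to support that assumption.

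**Conclusion.** The concern holds as a gap in the planned analysis. The main test of waning is valid in general only under an unstated missingness condition, which the study's own hypothesis gives reason to doubt if attendance depends on HIV control.

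The documents do not support concluding that HIV-related waning will be understated. That direction is plausible, but it depends on poorly controlled women leaving more often. If well-controlled women leave more, the sign reverses. Attrition in the HIV-negative cohort could also move the result.

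The 6% to 29% range is illustrative. It depends on the assumed dropout rates, on uncontrolled women having both lower titres and faster waning, and on the working correlation. The change is worth making before analysis because the needed data are already collected.

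**What to change.** Replace the unweighted GEE in item c) with an inverse-probability-of-attendance weighted GEE on log titre.

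- **Weights, HIV-positive cohort:** last observed titre, CD4 count, viral load, ART status, substance use and age. Sections 7.5.4 and 7.5.7.3 already provide for collecting the HIV and exposure data at visits.
- **Weights, HIV-negative cohort:** age and earlier titre where available.
- **Working correlation:** state it. Independence is the safer choice with visit-specific weights.
- **Non-return from CTN 236:** extend the weights to those of the 407 who do not join, using CTN 236 data.
- **Reporting:** compare leavers with stayers in both cohorts, and show the unweighted GEE alongside.

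An acceptable alternative is a likelihood-based mixed model on log titre that includes the Month 7 to 24 titres as earlier outcomes, with a time function that allows for the early fall from peak. It handles dropout explained by observed titres and model covariates. Mixed models already appear in the plan's exploratory analyses.

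The cost is some added analysis-plan text, a few extra models and slightly wider intervals. No new data are required. Chart follow-up after visits stop would be an optional extra and is not needed for this change.
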